
2. Protocol Narrative

a. Aims & Methodology

[figure not shown]
- a) **Aim 1:** To determine the effects of VLNC vs. NNC cigarettes on cigarettes smoked per day and frequency of alternative tobacco product use in adolescent cigarette smokers. We hypothesize that use of VLNC cigarettes will be associated with a decrease in combustible cigarettes smoked per day and an increase in the number of days of alternative combustible and noncombustible tobacco product use.
- b) **Aim 2:** To determine the effects of VLNC cigarettes on nicotine and toxicant exposure, perceived health risk of tobacco products, respiratory symptoms and dependence. We will test the hypothesis that use of VLNC cigarettes will lead to reduced nicotine and toxicant exposure, dependence, and respiratory symptoms in adolescent MTP users.
- c) **Aim 3:** To leverage real-time EMA assessment to determine the effects of VLNC cigarettes on withdrawal and craving, and to determine whether these momentary changes influence alternative tobacco use. We hypothesize that VLNC cigarette exposure may influence momentary changes in withdrawal and craving; and that these will vary both within and across individuals.

Impact of nicotine reduction on adolescent cigarette use, alternative tobacco use, and harm from tobacco

PIs: [name] & [name]

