b-c. Post-Session COVID survey and qualitative interview: Following the last sessions, participants will be asked if they would like to participate in a short survey and interview. They will first complete a brief survey of their COVID-19 experiences. Then, the researchers will conduct a recorded qualitative interview about their experiences with the EMA app in order to improve future app use.

11. Outcomes, Measures Justification, Descriptions, and Schedule

Primary Outcomes

- Cigarettes smoked per day
- Amount of total alternative product (ATP) use

Secondary Outcomes

- Amount of combustible and amount of noncombustible ATP use
- Toxicant exposure (total nicotine equivalents and NNAL)
- ~~FEV outcomes~~

Exploratory Outcomes

- ATSQ score
- Perceived Health Risk Questionnaire
- Nicotine dependence score
- Differences in craving across time and product type
- Differences in withdrawal across time and product type
- Measures of reinforcing efficacy/cigarette demand from the Cigarette Evaluation Scale
- Hypothetical Purchasing in the Experimental Tobacco Marketplace

Impact of nicotine reduction on adolescent cigarette use, alternative tobacco use, and harm from tobacco

PIs: [name] & [name]

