Analyses to address project aims. To address primary aims, 2-group (VLNC & NNC) x 2 repeated measures (Baseline & Week 4) mixed effects models tested the effect of the randomization group (VLNC vs. NNC) on change in cigarette use and alternative tobacco product (ATP) use from Baseline to Week 4. Similarly, to address secondary aims related to biomarkers of nicotine exposure, 2 x 2 mixed models tested the effects of VLNC vs. NNC cigarettes on change in biomarkers of nicotine exposure (i.e., total nicotine equivalents [TNEs] and cotinine), as well as average number study cigarettes smoked per day relative to average number of usual brand cigarettes smoked per day. In all models, Group (VLNC = 1; NNC = 0) was a between-subjects predictor, and Time (Baseline vs. Week 4) was the repeated measure. Subject was treated as a random effect to account for subject-level differences in baseline outcome levels. The focal tests evaluated the difference in change from Baseline to Week 4 (i.e., Time) in the VLNC vs. NNC condition (i.e., Group), which is a cross-level interactive effect of Time and Group. A *p*-value < 0.05 was interpreted as meeting statistical significance criteria. For all estimation

parameters, we report effect estimates, standard errors, and 95% confidence intervals in addition to p values.

Consistent with the original statistical analysis plan, demographics and baseline data on participant tobacco use history and individual characteristics were summarized using univariate descriptive statistics (e.g., means, standard deviations, frequencies). Data visualization and formal statistical evaluation of means, standard deviations, skewness, and kurtosis, assessed the distributional characteristics of each outcome. Where the assumptions of models implementing a normal (Gaussian) outcome distribution were not met, the statistical approach was revised accordingly. The following analytic procedures were required to meet model assumptions and account for skewed outcome distributions and low frequency events for certain outcomes.

1. Average cigarettes per day was positively skewed, with a non-normal residual distribution in a mixed model analysis specifying a normal (Gaussian) outcome distribution. Therefore, this outcome was recoded to integers and modeled as a count with a negative binomial distribution and log link.

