2. Frequencies of alternative product use (ATP) were low, particularly for combustible ATP use. Therefore, for the primary ATP outcome, combustible and non-combustible ATP use were modeled jointly and recoded as a dichotomous outcome (0 = <7 combined days of ATP use; 1 = 7+ combined days of ATP use), with a binary distribution and log link.
3. As secondary outcomes and to evaluate sensitivity, combustible and non-combustible ATP use were also considered independently as separate outcomes. Frequencies of combustible ATP use at Week 4 were too low to allow for model convergence. Frequencies of non-combustible alternative product use (ATP) were bimodal with peaks at 0 (no use) and 7 (daily use). Therefore, this outcome was recoded as a dichotomous outcome (0 = non-daily non-combustible ATP use; 1 = daily non-combustible ATP use) with a binary distribution and log link.
4. The study cigarette secondary outcome was modeled with a normal, Gaussian distribution. Baseline (Time = 0) in this analysis was average number of usual brand cigarettes at baseline,

prior to randomization, and Week 4 (Time = 1) was the average number of study cigarettes at Week 4.

5. Biomarker outcomes (i.e., total nicotine equivalents [TNEs] and cotinine) were modeled with normal, Gaussian distributions.

Missing data and sample size considerations. Missing data were assumed missing-at-random² (Whittaker, Pituch, & McDougall, 2014). Under the missing-at-random assumption, missing data for each focal variable is not expected to be related to that variable itself, e.g., a missed outcome assessment was not related to what that value would have been if it were assessed³ (Enders, 2006). The mixed model approach utilizing SAS software implemented restricted maximum likelihood estimation (continuous outcomes) and pseudolikelihood estimation (count and binary outcomes) to account for missing data. The mixed model reduces bias relative to other common approaches, particularly in cases where Group size is unbalanced due to attrition and/or baseline outcome levels differ between randomization groups.

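### Combustible alternative product use, a listed secondary outcome and part of Aim 1, has no specified analysis after its model failed to converge

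*SAP*

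**What the plan says.** **Protocol.** Section 2.a, Aim 1, hypothesises that VLNC cigarettes will be associated with "an increase in the number of days of alternative combustible and noncombustible tobacco product use". Section 11 lists among the secondary outcomes "Amount of combustible and amount of noncombustible ATP use". Section 6.e stratifies randomisation on past-month frequency of combustible ATP use, separately from non-combustible use.

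**SAP, Analyses to address project aims.** Item 2 notes that ATP frequencies were low, above all for combustible products. It responds by building the primary ATP outcome so that "combustible and non-combustible ATP use were modeled jointly and recoded as a dichotomous outcome", with the upper category "1 = 7+ combined days of ATP use". Item 3 then takes the classes apart: "As secondary outcomes and to evaluate sensitivity, combustible and non-combustible ATP use were also considered independently as separate outcomes". For the combustible class it reports "Frequencies of combustible ATP use at Week 4 were too low to allow for model convergence". The text moves directly to non-combustible use, which was bimodal and was recoded to a binary outcome ("1 = daily non-combustible ATP use") and modelled.

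The descriptive summaries that the SAP names are for baseline: "demographics and baseline data on participant tobacco use history and individual characteristics were summarized using univariate descriptive statistics". No Week 4 summary of combustible use by arm is specified.

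**The concern.** Sparse data can make a generalised mixed model fail, but they do not make the outcome unanalysable. Counts by arm, a risk difference with an exact or score-type interval, and penalised logistic regression are all available for this situation. The SAP names none of them.

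Protocol section 6.d says the trial models a policy in which nicotine reduction applies only to cigarettes. Whether participants move to other combustible products is therefore one of the questions it was set up to address. Without counts or an interval, a reader cannot tell whether use was rare in both arms and reasonably bounded, or whether the data were too thin to say anything.

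**Working it through.** The SAP gives no count, rate or estimate for combustible ATP use, so there is no figure of its own to reproduce. Its power statement concerns continuous EMA outcomes and does not bear on this point. The check has three steps.

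**1. How the SAP treats each tobacco-use outcome that did not suit a Gaussian model**

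| Outcome | Problem stated | Response stated |
|---|---|---|
| Cigarettes per day (item 1) | Positive skew | Integer count, negative binomial |
| Joint ATP use (item 2) | Low frequency | Binary, 7+ combined days |
| Non-combustible ATP use (item 3) | Bimodal at 0 and 7 days | Binary, daily vs non-daily |
| Combustible ATP use (item 3) | Too sparse to converge | None |

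Combustible use is the only one of the four without a stated alternative.

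**2. Whether the joint outcome can stand in for it**

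Consider two participants in the Week 4 TLFB week:

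- Vapes on all 7 days. Score = 1 with no cigarillo days, and still 1 with any number of them, so added combustible use does not change the score.
- Uses only combustible ATPs, on 1 to 6 days. Score = 0, the same as a non-user.

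The SAP does not say whether combined days are summed over the two classes or counted as calendar days with any use. Both results hold either way. Where combustible days do tip someone to 7 or more, the binary score does not show which class was responsible.

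**3. Whether an estimate is feasible with sparse counts**

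Assumptions, because the documents give neither counts nor the achieved N: 30, 45 or 60 analysed per arm (60 is the original target; the SAP says only that the total was reduced), and the user counts shown. The outcome is any combustible ATP use (1 or more days) in the Week 4 TLFB week.

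With 0 users of n in an arm, the Wilson upper limit is q²/(n + q²), where q = 1.96 and q² = 3.8415. With 0 in both arms the Newcombe interval for the risk difference is plus or minus that limit:

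- n = 60: 3.8415/63.8415 = 0.060
- n = 45: 3.8415/48.8415 = 0.079
- n = 30: 3.8415/33.8415 = 0.114

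Risk difference (VLNC minus NNC) with Newcombe 95% interval:

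| Users, VLNC vs NNC | 30 per arm | 45 per arm | 60 per arm |
|---|---|---|---|
| 0 vs 0 | 0 (−0.114 to 0.114) | 0 (−0.079 to 0.079) | 0 (−0.060 to 0.060) |
| 2 vs 0 | 0.067 (−0.057 to 0.213) | 0.044 (−0.041 to 0.148) | 0.033 (−0.032 to 0.114) |
| 3 vs 1 | 0.067 (−0.082 to 0.225) | 0.044 (−0.059 to 0.158) | 0.033 (−0.046 to 0.121) |
| 5 vs 2 | 0.100 (−0.074 to 0.276) | 0.067 (−0.055 to 0.195) | 0.050 (−0.043 to 0.150) |
| 6 vs 0 | 0.200 (0.045 to 0.373) | 0.133 (0.028 to 0.262) | 0.100 (0.020 to 0.201) |

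The risk difference and its interval are finite in every case, and wide in most.

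**The case against.** The strongest reply is that the SAP saw the sparsity and dealt with it. Item 2 pools the two classes because combustible use was rare, and this matches the protocol's primary outcome of total ATP use. Item 3 discloses the convergence failure and its cause. Both points stand. It would be wrong to infer that combustible use goes wholly unanalysed, or that the failure is hidden. What remains is that pooling answers a different question from the secondary outcome.

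A reader might also infer that only one model was tried, or that Week 4 counts will be withheld. The SAP says neither. It does not give the number of specifications attempted, and a results report could still show the counts. The supported statement is narrower: no fallback and no by-arm summary is specified.

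The SAP also prefers mixed models to baseline-covariate ANCOVA, citing missing outcomes and baseline imbalance, and retains everyone with Baseline data. A simple Week 4 comparison gives that up. This is a genuine cost of the fix, but the preferred model could not be fitted here.

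Finally, sparse-data methods have limits. With no events in either arm, the conditional exact odds ratio has no point estimate, and a Firth estimate comes from the penalty alone. This favours counts and a risk difference as the main report.

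**Conclusion.** The point holds as a modest gap in analysis and reporting for one sparse secondary outcome. As written, the SAP specifies no between-arm estimate for combustible ATP use, so that part of the Aim 1 hypothesis has no stated result. The primary analyses are unaffected. The omission can be read directly from the text; the interval widths rest on assumed counts and arm sizes.

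Two stronger readings are not supported.

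- **That the trial could detect large substitution.** Fisher's exact test at 45 per arm has 73% power for 2% vs 20% and 71% for 5% vs 25%. Those rates imply about 9 to 11 users in one arm (0.20 × 45 = 9; 0.25 × 45 = 11.25), which fits poorly with frequencies described as too low to model. Power falls to 15% for 2% vs 10% at 45 per arm, and to 41% for 2% vs 20% at 30 per arm.
- **That a single-arm limit bounds substitution.** Zero users among an assumed 50 gives an exact upper limit of 7.1%, but this limits prevalence in one arm. Every participant used some ATP at entry (protocol section 4.b), so a Week 4 combustible user may be continuing rather than switching. The between-arm difference is the relevant quantity.

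**What to change.** Add to SAP item 3, and carry into the results report:

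- The number and percentage with any combustible ATP use (1 or more days in the TLFB week), by arm, at Baseline and Week 4, with the number missing by arm.
- The Week 4 between-arm risk difference with one exact or score-type 95% interval.
- Optionally, a Firth-penalised logistic estimate for Group adjusted for baseline any-use.
- A label stating that this analysis is post hoc and, if the interval is wide, a statement that the combustible part of Aim 1 is inconclusive.

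The computing cost is a few lines of code on data already held. The statistical costs should be stated alongside the result: the any-use cut discards frequency information, the analysis uses only participants with Week 4 TLFB data, it targets a Week 4 difference rather than the Group by Time change used elsewhere, and the interval will be wide.

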Original power analyses suggested a target sample size of 120 participants (60 per Group) yielded sufficient power to detect effects of Group (VLNC vc. NNC) on change in cigarettes smoked and alternative products used, as measured via ecological momentary assessment (EMA). Specified population parameter estimates were based on prior literature^{4,5} and previous studies¹, and power was calculated to reflect a small to medium effect of VLNC vs. NNC on continuous (i.e., normally distributed) outcomes. For the direct effect of Group on primary outcomes, power to detect a small to medium direct effect (estimate = .15) with 120 participants (60 per Group) was .74 with 95% coverage, where power to detect a slightly larger effect (estimate = .20) was .96, with 95% coverage. Due to unforeseeable effects of the COVID-19 pandemic on data collection and unanticipated, intermittent challenges with the EMA software, the total number of participants was reduced, as was the degree of complete EMA data. As such, TLFB were utilized for an intent-to-treat analysis, thereby retaining all participants who provided Baseline outcome data.

1. [name] RN, Tidey JW, Jackson KM, et al. The Impact of Reducing Nicotine Content on Adolescent Cigarette Smoking and Nicotine Exposure: Results from a Randomized Controlled Trial. *Nicotine Tob Res Off J Soc Res Nicotine Tob*. Published online December 9, 2022:ntac279. doi:10.1093/ntr/ntac279
3. Enders CK. A primer on the use of modern missing-data methods in psychosomatic medicine research. *Psychosom Med*. 2006;68(3):427-436. doi:10.1097/01.psy.0000221275.75056.d8

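### Does the SAP need new power figures, and the achieved number per group, for its TLFB primary tests?

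*SAP*

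**What the plan says.** The power statement is in the SAP under Missing data and sample size considerations. The calculation is introduced as the original one, for outcomes measured by EMA, and "power was calculated to reflect a small to medium effect of VLNC vs. NNC on continuous (i.e., normally distributed) outcomes". The first result reads "power to detect a small to medium direct effect (estimate = .15) with 120 participants (60 per Group) was .74 with 95% coverage"; the second is .96 for an estimate of .20. The same paragraph then says that "the total number of participants was reduced, as was the degree of complete EMA data", and that TLFB data were used for an intent-to-treat analysis, "thereby retaining all participants who provided Baseline outcome data". No count is attached to that set.

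The primary tests are under Analyses to address project aims. Each compares the change from Baseline to Week 4 between groups. For cigarettes per day, "this outcome was recoded to integers and modeled as a count with a negative binomial distribution and log link". Alternative tobacco product (ATP) use is "recoded as a dichotomous outcome (0 = <7 combined days of ATP use; 1 = 7+ combined days of ATP use", with a log link. The section also commits that "we report effect estimates, standard errors, and 95% confidence intervals in addition to p values".

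The Protocol (section 3, Overall Study Design) gives the planned 60 per group and contains no power calculation.

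**The concern.** None of the conditions behind .74 and .96 holds for the primary tests. The data source changed from EMA to TLFB, the outcomes changed from continuous to count and binary, and the sample became smaller by an unstated amount. A split at seven combined days also carries less information than a count of days. The scale of the estimate, the sidedness and the alpha of the original calculation are not given, so the figures cannot be rebuilt either.

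What is at stake is how a null ATP result is read. Aim 1 in the Protocol (section 2a) expects "an increase in the number of days of alternative combustible and noncombustible tobacco product use". If the ATP test is not significant, a reader who looks for the trial's sensitivity finds only a statement that 120 participants gave enough power. That reader could take it as reassurance that very low nicotine cigarettes do not raise use of other products.

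**Working it through.** **1. Can the stated power be reproduced?** Inputs from the SAP: 60 per group; estimates .15 and .20; significance at p < 0.05. Two-sided testing is assumed. The scale of the estimate is not given, so several readings were tried by normal approximation:

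| Reading of the estimate | Power at .15 | Power at .20 |
|---|---|---|
| Standardized mean difference | .127 | .194 |
| Correlation, N = 120 | .373 | .592 |
| Cohen's f | .376 | .591 |
| f-squared | .989 | .998 |
| f on a change score, correlation .8 assumed | .738 | .934 |
| Stated in the SAP | .74 | .96 |

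No reading gives both figures. This does not show them to be wrong, because the longitudinal EMA model behind them is not described.

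**2. Effect of a smaller sample alone.** Hold each figure's implied standard error at 60 per group and rescale by sqrt(60/n).

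- Implied SE for .74: .15/(1.960 + .643) = .0576.
- Implied SE for .96: .20/(1.960 + 1.751) = .0539.
- n = 50: 2.603 × sqrt(50/60) − 1.960 = 0.416, power .66; 3.711 × sqrt(50/60) − 1.960 = 1.428, power .92.
- n = 40: 2.603 × sqrt(40/60) − 1.960 = 0.165, power .57; 3.711 × sqrt(40/60) − 1.960 = 1.070, power .86.

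The values 50 and 40 are assumptions. The two implied standard errors differ although the SAP presents one design, so these results are only a guide.

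**3. Could precision for the ATP test be stated from the documents?** For a log link with complete pairs, the standard error of the log ratio of risk ratios is sqrt(4(1 − p)(1 − φ)/(p n)). Here p is the proportion with seven or more days, φ the correlation between Baseline and Week 4, and n the number per group. The 95% interval is the estimate multiplied and divided by exp(1.96 SE). Neither p nor φ is in the documents.

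| Assumed p and φ | n = 60 | n = 40 |
|---|---|---|
| p = .5, φ = .7 | 1.32 | 1.40 |
| p = .3, φ = .3 | 1.91 | 2.21 |
| p = .2, φ = .3 | 2.33 | 2.82 |

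The last row at n = 60: sqrt(4 × .8 × .7/(.2 × 60)) = .432, and exp(1.96 × .432) = 2.33. It is included because the SAP describes ATP frequencies as low. Moving down a column changes the factor far more than moving across a row, so the unknown prevalence and correlation matter more than the unknown number per group. The formula is also a marginal approximation, whereas the SAP fits a subject random effect by pseudolikelihood.

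**4. What the SAP claims and what it supplies.** It calls the power calculation original, names its sample size, data source and outcome type, and then reports both departures. It nowhere claims that .74 or .96 applies to the TLFB tests. For those tests it promises an estimate, a standard error and a 95% interval.

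**The case for a change.** The strongest case for a change is that it is cheap. The SAP is dated 9/1/23 and written in the past tense, so the counts per group must have been known. A few sentences could give them, together with the scale of the estimate and a statement that a null ATP result will be read from its interval. The missing items are not redactions: the text passes from the reduced sample straight to the analysis set without a number.

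The factual part stands. The achieved number and the scale of the estimate are absent, and both would be useful to see. The claim of harm does not stand. Counts per group at each visit are normally reported with the results, and the SAP already defines the set to be counted. A sentence confining the original power to its own design would largely repeat what the paragraph says. Nothing in the documents proposes to read a null result from the original power, and the promised interval shows directly which increases in ATP use are excluded. A new power figure calculated after the data have been examined would add little to that interval.

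The difference between days of use in Aim 1 and the seven-day split is a separate question of outcome definition, and new power figures would not settle it.

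**Conclusion.** The observation is correct but no change to the plan follows. The figures .74 and .96 describe a design that was not carried through; the SAP says so openly and does not lend them to the final tests. What is missing is reporting detail that authors supply with the results. It alters no estimate, interval or test.

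The smaller sample alone would lower the original figures to roughly .66 and .92 at 50 per group, or .57 and .86 at 40, assuming two-sided .05 and those group sizes. For the binary ATP test, interval factors from 1.32 to 2.33 at 60 per group arise from plausible but assumed inputs. A null ATP result could therefore be inconclusive. The 95% confidence interval that the SAP already promises is the right place to see that, and a replacement power figure would not show it better.
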